4.3.3 Handling of Missing Data

In general, other than for the below described, or where otherwise specified in the particular analysis, missing data will not be imputed and will be treated as missing. The imputed dates should not be used to calculate durations, where the results would be less accurate.

4.3.3.1 Imputations of Partial Dates

- For missing diagnostic dates (eg, disease diagnosis), if the day and/or month are missing use 01 and/or January. if year is missing, put the complete date to missing.
- For missing concomitant medication and adverse events start dates, the following is applied:
 - Missing day: imputed with the 1st of the month, unless month and year are the same as month and year of first dose of IP, then impute with first dose date.
 - Missing day and month: imputed with the 1st of January unless the year is the same as the year of first dose of IP, then imputed with first dose date.
 - Completely missing: imputed with date of first dose of IP, unless the end date suggests it could have started prior to this in which case it is imputed 1st January of the same year as at the end date.

When imputing a start date care should be taken to ensure the start date is sensible, ie, prior to the end date.

- For missing concomitant medication and adverse events end dates, the following is applied:
 - Missing day: imputed with the last day of the month, unless both the month and year are the same as month and year of last dose of IP, or the primary analysis date cut-off (DCO) date then imputed with the last treatment date in that month or the primary analysis date cut-off (DCO) date.
 - Missing day and month: imputed with the 31st of December unless the year is the same as the year of last dose of IP or the primary analysis DCO date, then imputed with the last treatment date in that year or the primary analysis DCO date.
 - Completely missing: no date imputed (the event is assumed to be ongoing).

Flags will be retained in the database indicating where any programmatic imputation has been applied, and in such cases for AEs and concomitant medications, any durations will not be calculated.

4.3.4 Imputation Rules for Laboratory Values Outside of Quantification Range

Values of the form “< x” (ie, below the lower limit of quantification [LLQ]) or “> x” (ie, above the upper limit of quantification [ULQ]) will be imputed as “x” in the calculation of summary statistics but displayed as “< x” or “> x” in the listings.

4.4 Software

All report outputs will be produced using SAS® version 9.4 in a secure and validated environment. PK analyses will be produced using Phoenix® WinNonLin (WNL) version 8.1 or later in a secure and validated environment.

4.5 Analysis Sets

Details of the analysis sets are presented in [Table 2](#).

Table 2 Analysis Sets

Analysis Set	Definition
Enrolled	All subjects that signed the informed consent form (ICF).
Safety	All subjects who received any amount of AZD4573 and/or acalabrutinib. For safety analyses subjects will be reported by the actual treatment(s) received and grouped by their assigned target dose level of AZD4573.

Analysis Set	Definition
DLT-evaluable	
A DLT-evaluable subject is defined as a subject enrolled in the dose-setting part of the study (Part A) that has received AZD4573 in combination with acalabrutinib and either:
 
 Has received at least 3 doses of AZD4573 at the designated target dose level, has received at least 75% of acalabrutinib doses during the AZD4573 treatment weeks and has completed sufficient safety assessments (as determined by SRC review) through the DLT assessment period. 
The DLT-assessment period is assumed to have been completed with adequate safety assessments for SRC evaluations if 3 doses of AZD4573 were received at the designated target dose level. In case of an extended DLT period (longer than 5 weeks), where there has been AZD4573 dose interruption(s), the requirement for at least 75% of planned acalabrutinib doses will be applicable only to AZD4573 treatment weeks. If the time period between two consecutive AZD4573 infusion dates does not exceed 9 days, the AZD4573 treatment week is defined as: from the day of AZD4573 infusion until the 9th day or the next AZD4573 infusion, whichever comes first. In case the next AZD4573 dose was administered \geq 10 days after the previous AZD4573 dose, the AZD4573 treatment week is defined as: from the day of AZD4573 infusion until the 7th day.
 
Or
 
 Has experienced a DLT during the DLT-assessment period. (For analysis reporting purposes, the DLTs are as approved and documented at the Safety Review Committee meetings.) 
This excludes a subject that is part of the backfill. If a subject is assigned to Part A in Module 1 and has an ICF signed after CCI (the date of the SRC when RP2D was declared, and decisions were made to open Part B and backfill Part A), then he/she is considered backfill.

Pharmacokinetics (PK)	All dosed subjects with reportable plasma concentration and no important protocol deviations that may impact PK. Subjects will be reported by the actual treatment(s) received and grouped by their assigned target dose level of AZD4573.
Response evaluable	Subjects dosed with AZD4573 or acalabrutinib with measurable disease (longest diameter greater than zero) at baseline.

Analysis Set	Definition
Interim response evaluable	Subjects dosed with AZD4573 or acalabrutinib, or both AZD4573 and acalabrutinib with baseline tumour assessment and have their first post-baseline disease assessment performed or have discontinued study treatment for any reasons before their first post-baseline disease assessment.
Full Analysis Set (ITT)	All subjects who received any amount of AZD4573 and/or acalabrutinib.

Abbreviations: DLT = dose-limiting toxicity; ICF = informed consent form; ITT intention-to-treat;

PK=pharmacokinetics.

Upon database release, protocol deviations and analysis set outputs will be produced and will be sent to AZ for review. Prior to database lock for the primary analysis, an analysis set classification meeting will be arranged to discuss the outputs and to decide which subjects and/or subject data will be excluded from certain analyses. Decisions made regarding the exclusion of subjects and/or subject data from analyses will be made prior to primary analysis lock and will be documented and approved by AZ.

A summary on which analysis set will be used for each outcome variable is provided in [Table 3](#).

Table 3 Summary of outcome variables and analysis sets

Outcome Variable	Analysis Set
Study Population/Demography Data	
Disposition	All Subjects
Demography and baseline characteristics	FAS
Important protocol deviations	FAS
Medical History	FAS
Prior/Concomitant Medication	FAS
Safety data	
Exposure	Safety
Adverse Events	Safety
Laboratory measurements	Safety
Vital Signs/ECG/Physical examination	Safety
ECOG PS	Safety
DLTs	DLT evaluable
Efficacy Data	
CR rate	Response evaluable
TTR	Response evaluable
DoR	Response evaluable

Outcome Variable	Analysis Set
PFS	FAS
OS	FAS
ORR	Response evaluable
Pharmacokinetics	
Pharmacokinetic variables	PK

Abbreviations: CRR = Complete response rate; DLT = dose-limiting toxicity; DoR = duration of response; ECOG PS= Eastern Co-operative Oncology Group performance status; FAS = full analysis set; ORR = objective response rate; OS = overall survival; PFS = progression free survival; PK = pharmacokinetic; TTR: = time to objective response.

The number of enrolled subjects included/excluded from each of the analysis sets will be summarised. Subjects and data excluded from each analysis set will be listed with the reason for exclusion.

4.6 Study Subjects

4.6.1 Disposition of Subjects

Module 1 – Part A and Part B:

Subject disposition from screening to study completion will be listed and summarised for all subjects. Summaries will include:

- Number of subjects enrolled (informed consent received)
- Number of screen failures (including reasons)
- Number and percentage of subjects who received treatment (including reasons for those that did not receive treatment)
- Number and percentage of subjects ongoing in the study at data cut-off (DCO)
- Number and percentage of subjects ongoing treatment at DCO
- Number and percentage of subjects who discontinued treatment (including reasons for discontinuation)
- Number and percentage of subjects who terminated study

Subject discontinuations will be listed, including dose level/cohort, the date of study exit, total treatment duration (days), actual treatment duration (days) and reason for discontinuation. Total treatment duration and actual treatment duration will be derived as described in [Section 4.11.1](#).

Summaries on disposition due to COVID-19 will be added to the disposition table if applicable. The number and percentage of subjects for the following summaries will be added if applicable:

- Subjects who discontinue intervention due to COVID-19;
- Subjects who withdrew from study due to COVID-19.

The number and percentages of subjects with confirmed or suspected COVID-19 infection will be presented separately, including details on COVID-19 related interruptions impacting visits and IP administration. Listings of subjects affected by the COVID 19 pandemic will be presented detailing

any affect and impact on the study. Issues reported in the Clinical Trial Management System will be considered for presentation in listings as well.

As supportive analysis, all enrolled subjects will be presented in a listing indicating the different analysis sets in which these are included and flagging all those belonging to the backfill cohorts, this latter category includes all subjects enrolled after SRC **CCI**

Module 2:

All subjects enrolled in Module 2 will be presented, including the enrollment into Period 1 and Period 2. In addition, subjects who discontinued study and /or affected by Global/country situation will be appropriately listed.

4.6.2 Protocol Deviations

Important protocol deviations are defined as those deviations from the protocol likely to have an impact on the perceived efficacy and/or safety of study intervention. Protocol deviations will be collected and classified as defined in the protocol deviations specification. The final assessment of Protocol Deviations will be performed at a Data Review Meeting (DRM) shortly before database lock. Results and population assignments will be summarized in a DRM report which will be signed off by all relevant scientific experts.

The following general deviation categories will be defined. These deviations will be reviewed on a case-by-case basis by AstraZeneca to determine importance. Deviations considered to be important will be listed and discussed in the CSR as appropriate. All decisions on importance will be made ahead of database lock and will be documented prior to the primary analysis being performed.

- Subjects who deviate from entry criteria per CSP
- No baseline Lugano assessments on or before the date of first dose
- Received prohibited concomitant medications or therapies.
- Subjects deviating from prescribed dosing regimen.
- Missed visits, assessments, or treatments that, in the opinion of the investigator, were due to Coronavirus Disease 2019 (COVID-19) global pandemic, and where there was a significant effect on either completeness, accuracy and/or reliability of the subject's data, or the subject's rights, safety or wellbeing.
- Missing scheduled efficacy assessments
- Deviation from Good Clinical Practice as determined by medical review (for example insufficient informed consent)

The important protocol deviations affecting Module 1 subjects will be listed and summarised by dose level on the Full Analysis Set. Important protocol deviations related to COVID-19 will be summarised separately.

The important protocol deviations affecting Module 2 subjects will be only presented in a listing.

A full list of protocol deviations can be found in the study-specific Protocol Deviation Specification. Protocol deviations will be reviewed on a regular basis between AZ and Parexel Data Operations.

4.7 Demographics and Baseline Characteristics

Demographic and baseline characteristics will be summarised and listed for all subjects in the Safety Analysis Set by dose level/cohort:

- Demographic characteristics (age[years], age group [(≥ 18 - 64, ≥ 65 - 74, ≥ 75 - 84, ≥ 85)], sex [female; male], race, ethnicity and country).
- Subject characteristics at baseline (height[cm], weight [kg], and body mass index [BMI] [kg/m²]).
- Previous disease related treatment modalities by preferred group.
- Any other subject/disease characteristics at baseline as specified below.

Subject/disease characteristics at baseline:

- Eastern Cooperative Oncology Group (ECOG) performance status
- Histology type
- Lymphoma classification
- Lugano Modification of Ann Arbor Staging
- International Prognosis Index (IPI) score
- Brain involvement
- Spleen involvement
- Bone marrow involvement
- Liver involvement
- Extranodal involvement
- Bulky nodal disease
- Histology subtype /cell of origin (COO)

The histology subtype will be assigned by local sites for Module 1 Part A GCB and non-GCB subjects who are treated at RP2D (refer to the subject recycling process document) and all Module 1 Part B subjects.

Demographics and subject characteristics will further be summarised separately for all subjects in the FAS who had confirmed or suspected COVID-19 infection. If less than 5 subjects have confirmed or suspected COVID-19 infection, this will be presented in a listing rather than being summarised.

4.8 Medical/Surgical History

Medical history and surgical history will be coded using Medical Dictionary for Regulatory Activities (MedDRA) version 24.1 (as a minimum). Disease related medical history will be listed and the number and percentage of subjects with any disease related medical history will be summarised for

the Safety Analysis Set by system organ class (SOC) and preferred term (PT), by dose level/cohort and overall.

Surgical history will be listed and summarised similarly.

A separate summary on medical history will be presented for subjects who had confirmed or suspected COVID-19 infection. If less than 5 subjects have confirmed or suspected COVID-19 infection, this will be presented in a listing rather than being summarised.

4.9 Concomitant Medications and Other Treatments

Treatments received prior to, concomitantly or post-treatment will be coded using the World Health Organisation-Drug Dictionary (WHODRUG) and will be classified by Anatomical Therapeutic Chemical (ATC) categories.

For inclusion in prior and/or concomitant medication or therapy summaries, incomplete medication or radiotherapy start and stop dates will be imputed as detailed in [Section 4.3.2](#).

Prior medications, concomitant and post- medications are defined based on imputed start and stop dates as follows:

- Prior medications are those that started and stopped prior to the first dose of the IP.
- Concomitant medications are those with a stop date on or after the first dose date of IP (and could have started prior to or during treatment).
- Post medications are those with a start date after the last dose of the IP.

All concomitant medication will be listed by subject and will include the reported name, PT, ATC, route of administration, dose, frequency, start date/time, duration and indication and will be summarised by ATC and PT, dose level/cohort.

Radiotherapy and cancer therapies prior to the study will be listed.

The following summaries will be produced:

- Previous cancer therapies
- Lines of previous cancer therapies
- Previous chemotherapy
- All concomitant medications

Post-discontinuation cancer therapies will be listed.

All prior, concomitant and post IP medication data (including surgical procedures) will be listed.

Missing coding terms (ATC or Preferred term [PT]) will be listed and summarised as uncoded terms.

All listings and tables will be based on the Safety Analysis Set.

4.10 Efficacy Evaluation

Module 1:

Module 1 Parts A and B include the following efficacy endpoints: objective response rate (defined as the proportion of subjects who have a tumour response [CR or PR] by investigator assessment), CR rate, TTR, DoR, PFS and OS.

All assessments of anti-tumour activity will be done by the investigators using standard response criteria as specified in Section 17.4 of the CSP.

Initial disease assessment for DLBCL include staging by Ann Arbor classification.

Tumour assessments will be made for measurable disease, non-measurable disease, and new lesions on CT and combined with visual assessment of PET-CT for response assessment according to the revised response criteria for malignant lymphoma (refer to Table 17 of CSP).

All response assessments will be made by the investigator. All images for the assessment of response will be collected and stored for potential central review. Additional disease assessments may be performed as clinically indicated.

The following tumour assessment details will be listed by subject:

- Target lesion size
- Non-target lesion
- New lesion
- Spleen/Liver Disease

Module 2:

For Module 2 subjects, all figures and listings will be based on the FAS or Safety analysis sets, except the Response assessment figure that will be based on the Response Evaluable set. Data will appropriately be listed by treatment period.

4.10.1 Analysis and Data Conventions

No hypotheses are planned to be tested.

4.10.1.1 Multi-centre Studies

No adjustments for center will be performed.

4.10.1.2 Adjustments for Covariates

No adjustments for covariates will be performed.

4.10.1.3 Handling of Dropouts or Missing Data

Summary statistics will be based on non-missing values unless otherwise specified.

4.10.2 Primary Efficacy Endpoint

In Module 1 Part B, the primary efficacy endpoint is the objective response rate (ORR). Primary efficacy endpoint will be analysed and presented by dose level.

4.10.2.1 Objective response rate (ORR)

The ORR is defined as the proportion of subjects who achieve either a partial response (PR) or complete response (CR) as determined by the investigator at local site per Lugano criteria prior to any evidence of progression and will be based on the response evaluable set, all subjects who received any amount of AZD4573 and acalabrutinib with measurable disease at baseline. A response does not need to be confirmed to be included in the calculation of ORR.

Data obtained from first dose up until progression, or the last evaluable assessment in the absence of progression, will be included in the assessment of ORR, regardless of whether the subject withdraws from therapy. Subjects who discontinue study treatment without a response or progression, receive a subsequent anti-cancer therapy and then respond will not be included as responders in the ORR (ie, the visit contributing to a response must be prior to subsequent therapy for the subject to be considered as a responder).

The ORR will be based on the investigator Lugano data and using all scans regardless of whether they were scheduled or not.

Summaries will be produced that present the number and percentage of subjects with a tumour response (CR or PR) based upon the number of subjects with measurable disease at baseline per investigator. ORR will be calculated and binomial exact 2-sided confidence intervals (CIs) at 80% and 95% will be presented for subjects in the Response Evaluable Set.

Best overall response (BoR)

BoR is calculated based on the overall visit responses from Lugano assessments by the investigator recorded in the eCRF. It is the best overall response a subject has had following start of study treatment, but prior to starting any subsequent cancer therapy and up to and including Lugano progression or the latest evaluable assessment in the absence of Lugano progression. Categories of BoR will be based on Lugano criteria using the following response categories (CR, PR, SD, PD and NE).

BoR will be summarised by number of subjects and percentage for each category (CR, PR, SD, PD, and NE). No formal statistical analyses are planned for BoR.

4.10.3 Other Efficacy Variables

In Module 1 Part A and Module 2, all efficacy endpoints are exploratory. In Module 1 Part B, all efficacy endpoints other than ORR are secondary.

All listings and summaries will be based on the Response Evaluable Set, except PFS and OS that will be based on the FAS as defined in [Table 3](#).

Tumour response data will be listed and summarised by dose level, if appropriate, using the Lugano Response Criteria for Non-Hodgkin's Lymphoma in Table 17 of the CSP.

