A summary of censoring rules and the date of PD/death or censoring are given in [Table 4](#). Note that censoring overrides event in certain specified cases.

Table 4 Summary of Censoring Rules for PFS

Situation	Date of PD/Death or Censoring	PFS Outcome
Documented Progressive Disease (PD) or death in the absence of progression	Date of earliest documentation of PD or date of death in the absence of progression	Event
Either no tumour assessment at baseline or no evaluable assessments post-baseline	Date of death	Event

Table 4 Summary of Censoring Rules for PFS

Situation	Date of PD/Death or Censoring	PFS Outcome
AND death prior to second scheduled post-baseline disease assessment		
Either no tumour assessment at baseline or no evaluable assessments post-baseline AND no Death prior to second scheduled post-baseline disease assessment	Date of first dose (Day 1)	Censored
PD or death (in the absence of progression) immediately after ≥ 2 consecutive missed disease assessments as per the protocol specified assessment schedule	Last evaluable progression-free disease assessment prior to missed assessments	Censored
On-going with neither PD nor death at the time of analysis or lost to follow-up or withdrawn consent	Date of last evaluable disease assessment	Censored

Abbreviations: PD = progressive disease; PFS = progression-free survival.

The PFS time is always derived based on scan/assessment dates, not visit dates.

Disease assessments/scans contributing towards a particular visit may be performed on different dates. The following rules are applied:

- The date of progression is determined based on the earliest of the dates of the component that triggered the progression.
- When censoring a subject for PFS the subject is censored at the latest of the dates contributing to a particular overall visit assessment.

Note: for target lesions only the latest scan date is recorded out of all scans performed at that assessment for the target lesions and similarly for non-target lesions only the latest scan date is recorded out of all scans performed at that assessment for the non-target lesions

The main analysis of PFS is based on the FAS. The number and percentage of subjects experiencing a PFS event [broken down by type of event/censoring] and Kaplan-Meier plots of PFS will be presented. The median PFS and its 2-sided 80% and 95% confidence intervals will be estimated using the Kaplan-Meier method (if subject numbers allow).

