The analysis of OS is based on the FAS. The number and percentage of subjects experiencing an OS event and Kaplan-Meier plots of OS will be presented. If subject numbers allow, the median OS and 2-sided 80% and 95% CI will be estimated using the Kaplan-Meier method.

Summaries of the number and percentage of subjects who have died, those still in survival follow-up, those lost to follow-up and those who have withdrawn consent will be provided.

A summary of the duration of follow-up for OS will be included using median (range). This will be presented separately for censored and non-censored subjects.

Duration of follow-up for OS is reported separately for censored subjects and non-censored subjects and is defined as follows:

Duration of follow-up for OS (months) = (date of death or censoring (date last known to be alive) – date of first dose + 1) / (365.25/12).

The proportion of subjects alive at every 3 months (3, 6, 9, 12) and associated 2 sided 80% and 95% CIs will be estimated using the Kaplan-Meier method.

Supportive data: Change in Target Lesion Tumour Size

Target lesions are measurable tumour lesions. Baseline is defined to be the last evaluable assessment prior to starting treatment.

Target lesion tumour size for the target measurable nodes and extra-nodal sites at any timepoint is defined as the sum of the product of the perpendicular diameters for multiple lesions. When a lesion is too small to measure, 5 mm x 5 mm will be assigned as the product of the perpendicular diameters.

If target lesion measurements are missing post-baseline, then the sum of the product of perpendicular diameters for multiple lesions will be set to missing for that post-baseline measurements. Subsequent percentage changes will consequently not be calculated using post-baseline measurements where any target lesion measurement is missing.

The percentage change in target lesion size at each timepoint for which data are available will be obtained for each subject, taking the difference between each timepoint and baseline multiplied by 100 (ie, [timepoint – baseline]/baseline x 100).

The best change in tumour size from baseline (ie, depth of response) is the largest decrease from baseline or the smallest increase from baseline in the absence of a reduction and includes all assessments:

- up to and including the first visit at which the overall visit response is a PD,
- prior to death in the absence of progression,

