6 APPENDICES

Module 1 - Part A subjects to be included in Part B analysis

PURPOSE:

This document describes the process for using data from subjects enrolled in Module 1 Part A in analyses for Module 1 Part B. This document describes:

- the process for Cell of Origin (COO) testing, used to identify GCB and non-GCB DLBCL subjects;
- the selection criteria for Part A subjects whose data will be included in the final analysis for Part B;
- the process to document the recycling of Part A subjects data.

PROCESS

1. Cell of Origin (for all part A and part B subjects)

For the purposes of recycling of data from Part A subjects for analysis with Part B subjects data, COO data from local assessment will be used.

2. Definition of Part A subjects that will be included in the Module 1 Part B final analysis

Data from Module 1 Part A subjects will be analysed together with data from Part B subjects if the Part A subjects fulfil all the conditions below:

- Must have received any amount of AZD4573 and acalabrutinib on study;
- Must have been enrolled in the 12 mg (RP2D) dose level cohort;
- Must have a diagnosis of de novo DLBCL, ie:
 - DLBCL NOS (de novo), or
 - High-Grade B cell Lymphoma (NOS), or
 - High-Grade B cell Lymphoma with MYC and BCL2 and/or BCL6 rearrangements;
- Must have measurable disease at baseline (ie be part of the response evaluable set).

3. Documentation of review and confirmation

The Parexel Programming team will programmatically identify Part A subjects whose data can be recycled in Part B for final analysis purposes, based on the criteria described in this document.

Subjects that can be recycled will be marked by population flags in the ADAM and SDTM specifications. TFLs will be generated including the correct individuals (including recycled subjects) in each cohort; a listing of recycled subjects will also be included in the TFLs.

SIGNATURE PAGE

This is a representation of an electronic record that was signed electronically and this page is the manifestation of the electronic signature

Document Name: d8230c00002-sap-ed-5		
Document Title:	Statistical Analysis Plan Edition 5	
Document ID:	Doc ID-004599196	
Version Label:	5.0 CURRENT LATEST APPROVED	
Server Date (dd-MMM-yyyy HH:mm 'UTC'Z)	Signed by	Meaning of Signature
30-Oct-2023 14:53 UTC	PPD 	Content Approval

Notes: (1) Document details as stored in ANGEL, an AstraZeneca document management system.

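### Part B PFS and OS are assigned to the FAS, but the appendix lets Part A subjects into Part B only if they received both drugs and are response evaluable, so Part B cohort outputs can mix two entry rules

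*SAP*

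**What the plan says.** Section 4.10.3 sets the analysis sets for the efficacy variables other than ORR: "All listings and summaries will be based on the Response Evaluable Set, except PFS and OS that will be based on the FAS". Table 3 agrees, section 4.10.3.4 adds that "The main analysis of PFS is based on the FAS", and section 4.10.3.5 that "The analysis of OS is based on the FAS". Table 2 in section 4.5 defines the FAS as "All subjects who received any amount of AZD4573 and/or acalabrutinib". It has no measurable-disease condition.

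The appendix decides which Part A subjects are analysed with Part B. It pools them "if the Part A subjects fulfil all the conditions below". Besides a listed de novo DLBCL diagnosis, the conditions are:

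- "Must have received any amount of AZD4573 and acalabrutinib on study"
- "Must have been enrolled in the 12 mg (RP2D) dose level cohort"
- "Must have measurable disease at baseline (ie be part of the response evaluable set")

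The appendix names no endpoint to which these conditions do not apply. It says that recycled subjects will be identified by program, flagged, and included in the cohort outputs.

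Section 4.2 states the recycling rule differently: RP2D-treated Part A subjects who meet the Part B entry criteria. It mentions neither receipt of both drugs nor response evaluability. It also makes dose level, with Parts A and B combined, the default layout for Module 1 summary tables.

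**The concern.** Section 4.10.3 deliberately puts PFS and OS on the wider set. A single recycling flag built from the appendix brings the narrower set back for the Part A contribution. A Part B cohort estimate of PFS or OS, labelled as an FAS result, would then hold directly enrolled subjects admitted on any amount of either drug and recycled subjects admitted on a stricter test.

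The both-drugs condition is the more troublesome one. PFS and OS are counted from first dose. Whether a subject ever received the second drug can be settled after that date, by stopping or dying early. Conditioning on it selects subjects by what happened during follow-up. At stake are the secondary PFS and OS estimates for Part B: a few early failures could leave the denominator without the output showing it.

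**Working it through.** The SAP states no sample size, event count or power for this point (section 4.13 refers to the protocol), and section 4.10.1 says that no hypotheses are tested. There is no plan figure to reproduce. The check compares the rules and then illustrates the size.

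**Entry rules compared**

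| Condition | Enrolled directly in Part B, FAS (Table 2) | Recycled from Part A (appendix) |
|---|---|---|
| Drug received | any amount of either | any amount of both |
| Measurable disease at baseline | not required by the FAS | required |
| Dose | not part of the FAS definition | enrolled in the 12 mg cohort |

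**Who is dropped**

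1. A 12 mg Part A subject with a listed diagnosis who stopped or died after receiving only one drug. This subject is in the FAS and counts for PFS and OS, but fails the both-drugs condition.
2. A 12 mg Part A subject with no baseline tumour data, who cannot be shown to have measurable disease. Section 4.10.3.4 and Table 4 keep such a subject in PFS. A death within 8 + 9 + 1 = 18 weeks is a PFS event; otherwise the subject is censored at Day 1. Dropping this subject removes a PFS event only if death came early. For OS, the subject's whole follow-up is lost.
3. A 12 mg Part A subject assessed at baseline but with no measurable lesion.

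**Who is not dropped**

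- A subject with measurable disease who failed before the first scan: the Response Evaluable Set in Table 2 needs no post-baseline assessment.
- A subject who took some of both drugs and failed during ramp-up: the dose condition is enrolment in the 12 mg cohort, not receipt of 12 mg.

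**Size, on assumed inputs**

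Let N be the pooled Part B FAS with nobody dropped, x the number event-free at a landmark, and k the number of early failures dropped. Censoring is ignored. The shift is x/(N − k) − x/N. N, x and k are all assumptions.

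| N | x | k = 0 | k = 1 | k = 2 | k = 3 |
|---|---|---|---|---|---|
| 20 | 12 | 60.0% | 63.2% | 66.7% | 70.6% |
| 30 | 12 | 40.0% | 41.4% | 42.9% | 44.4% |
| 40 | 8 | 20.0% | 20.5% | 21.1% | 21.6% |

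For N from 20 to 40 and an event-free share from 20% to 60%, the first and last rows give the largest and smallest shifts: 0.5 to 3.2 points for one subject dropped, 1.1 to 6.7 for two, and 1.6 to 10.6 for three. With k = 0 the shift is zero. For scale, the exact 95% interval for 12/30 runs from about 23% to 59%, so one or two dropped subjects move the estimate by much less than its sampling uncertainty.

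**The case against.** Four points can be made on the other side.

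- **The default layout avoids the problem.** Section 4.2 combines Parts A and B by dose level unless otherwise stated. A 12 mg Part A subject stays in the 12 mg column whether recycled or not. This stands, and it confines the point to Part B cohort or subgroup outputs.
- **Measurable disease may already be a Part B entry criterion.** Those criteria are in the protocol, which is not at hand. If they require it, both groups meet the same standard on this condition and that half of the discrepancy largely disappears. This also stands.
- **Single-drug subjects may not exist.** Section 3.3.2 derives PK parameters for both drugs from Cycle 1 Day 1 of Week 1, which suggests near-simultaneous starts. This makes small numbers likely but does not rule such subjects out.
- **The estimates are descriptive and recycled subjects are listed.** True, but that listing does not show who was left out or why.

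A reader might infer that safety at the RP2D is also distorted. The documents do not support this. Section 4.11 puts safety tables other than DLT tables on the Safety set, Table 2 groups that set by assigned target dose, and the pooled RP2D summary of DLT-like events in section 4.11.3 has its own condition of three doses at target level. A reader might also infer that the rule is shown to flatter the combination. It is not shown: no counts are given, and lack of measurable disease is a baseline feature whose effect on PFS or OS the SAP does not state.

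**Conclusion.** The inconsistency is real and lies within the SAP. PFS and OS are assigned to the FAS, while the recycling rule carries the both-drugs and Response Evaluable conditions into the Part A contribution with no exception for these endpoints. Followed as written, Part B cohort or subgroup outputs for PFS and OS would have two entry standards, one of which can depend on events after first dose.

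The likely effect is small and may be zero. If anyone is dropped on the both-drugs condition, the shift would probably favour the combination, because those who received only one drug are likely to have stopped or died early. No direction is established for the measurable-disease condition, which matters only if the Part B entry criteria do not already require measurable disease. The point concerns descriptive secondary estimates and no test. It is worth correcting because the correction is cheap and makes the Part B PFS and OS outputs what section 4.10.3 says they are.

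**What to change.** In the appendix, split the recycling rule by endpoint.

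- **Part B PFS and OS:** recycle Part A subjects in the 12 mg cohort who have a listed diagnosis, meet the Part B entry criteria as section 4.2 requires, and are in the FAS. Drop the both-drugs condition. Keeping the entry criteria matters, since otherwise the change could bring in subjects not eligible for Part B.
- **ORR, CR rate, TTR and DoR:** keep the Response Evaluable condition. Reconcile its wording at the same time: Table 2 says either drug, section 4.10.2.1 says both.
- **Flags and listing:** carry two recycling flags, and list the 12 mg Part A subjects who are not recycled, with the reason.

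The cost is SAP wording and one extra flag. Part B PFS or OS may look slightly less favourable.
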